H&P	History & Physical Exam
HRQOL	Health-related Quality of Life
HRPP	Human Research Protections Program
IHC	Immunohistochemistry
IV (or iv)	Intravenously
mRCC	Metastatic Renal Cell Cancer
MTD	Maximum Tolerated Dose
NCI	National Cancer Institute
ORR	Overall Response Rate
OS	Overall Survival
PBMCs	Peripheral Blood Mononuclear Cells
PD	Progressive Disease
PFS	Progression Free Survival
p.o.	Per os/by mouth/orally
PR	Partial Response
PRN	“Pro re nata” or as needed
QoL	Quality of Life
RR	Response Rate
RT	Room Temperature
SAbR	Stereotactic Ablative Body Radiotherapy
SAE	Serious Adverse Event
SBRT	Stereotactic Body Radiation Therapy
SD	Stable Disease
VAS	Visual Acuity Score
WBC	White Blood Cells

STUDY SCHEMA

STUDY SUMMARY

Title	Phase II Trial of Nivolumab and Stereotactic Ablative Radiation Therapy (SAbR) for Metastatic Clear Cell Renal Cell Carcinoma (mRCC)
Short Title	Nivolumab and SABR for metastatic RCC
Protocol Number	STU 122015-052
Phase	Phase II
Methodology	Single arm
Study Duration	8 years (5 years for enrollment and 3 years for follow-up).
Study Center(s)	Single-center at UTSW
Objectives	To evaluate safety and response rate (RR) of mRCC after treatment with SAbR and Nivolumab
Number of Subjects	21 patients
Diagnosis and Main Inclusion Criteria	Metastatic Clear Cell Renal Cell Carcinoma patients who have failed one anti-angiogenic therapy
Study Product(s), Dose, Route, Regimen	Nivolumab (brand name Opdivo): Nivolumab administered per standard of care according to institutional guidelines. The standard FDA approved administration and indications of Nivolumab is listed in the FDA website: www.fda.gov or Package Insert https://www.accessdata.fda.gov/drugsatfda_docs/label/2018/125554s058lbl.pdf ; SABR, dose variable, in 1-3 fractions.
Duration of administration	Nivolumab: Nivolumab administered per standard of care according to institutional guidelines. The standard FDA approved administration and indications of Nivolumab is listed in the FDA website: https://www.accessdata.fda.gov/drugsatfda_docs/label/2018/125554s058lbl.pdf ; SABR: 1-3 fractions over one week.
Reference therapy	Nivolumab alone from published historical control phase III study
Statistical Methodology	Exact binomial test will be used to investigate if the response rate of the treatment arm is significantly different from that of the historical control. One-sample log-rank tests will be conducted to examine if OS or PFS in the treatment arm is significantly different from that of the historical control.

1.0 BACKGROUND AND RATIONALE

1.1 Disease Background

An estimated 64,770 cases of kidney cancer (RCC) will be diagnosed in the U.S. in 2012 with an estimated 13,570 deaths (SEER). There has been a steady 2-4% per year increase in the incidence of RCC since 1975 that is not explained by increased and improved imaging studies. Clear cell cancers are the most common variant of kidney cancers comprising up to 80% of RCC. The five-year survival rate for RCC patients is 70%, however, this is including the majority of patients with localized disease whose five-year survival is 91%. At the time of diagnosis approximately 30% of RCC patients have metastatic disease and another 30% of patients recur, whose five-year survival is less than 10%. Therefore, there remains a great need for improvement in the therapeutic management of metastatic clear cell RCC (mRCC).

RCC is a unique cancer that is well known for its immunogenicity. It is one of the first cancers in which immunostimulatory therapy, such as interferon and interleukin, has been shown to induce durable treatment response leading to FDA approval of HD IL-2 treatment for mRCC patients as early as 1992. A number of targeted therapies have been recently approved for the treatment of mRCC including vascular endothelial growth factor (VEGF) pathway inhibitors [1-3], mammalian target of rapamycin (mTOR) inhibitors [4], and most recently programmed death 1 (PD-1) inhibitor Nivolumab [5]. Complete response remains rare even with immunotherapies. Strategies for enhancing the percentage of patients exhibiting a CR may prove to be the only hope in offering a definitive treatment for this patient population.

1.2 Stereotactic Ablative Body Radiation (SABR)

Stereotactic ablative body radiation (SABR) is an emerging treatment paradigm defined in the American Society of Therapeutic Radiology and Oncology guidelines as a “treatment method to deliver a high dose of radiation to the target, utilizing either a single dose or a small number of fractions with a high degree of precision within the body” [6]. Potential indications for SABR include a broad spectrum of tumor types and locations. The safety and efficacy of SABR to multiple sites is excellent as documented in multiple studies [7-9].

Previous studies have demonstrated multiple immunogenic properties of radiation therapy, especially when given at high doses such as with SABR [10, 11]. Since SABR is a highly focused therapy, it does not inherently immunocompromise the host. In addition, as opposed to conventional radiation fields, SABR is a highly focused therapy that spares the surrounding lymph nodes which are vital for an effective immune response. By not surgically removing the tumor, the body retains the antigen depot (dying tumor cells) within the host. Furthermore, since SABR causes local inflammation, dendritic cells (DCs) are attracted into the tumor. The antigen-presenting properties and the induction of immunogenic cell death by SABR are well documented [12]. SABR-induced tumor cell death is primarily via mitotic catastrophe or necrosis, both of which are known to be immunogenic cell deaths as opposed to apoptosis, which is immunologically tolerogenic [13]. *In vivo* studies have shown that radiation induces release of damage (or danger)-associated molecular patterns (DAMPs) such as HMGB1, HSP and calreticulin into the extracellular matrix and thereby promotes the recruitment and activation of antigen-presenting cells (APCs) such as DCs for antigen presentation [14-16]. Subsequently, the APCs migrate to the draining lymph nodes for the presentation of the antigens and efficiently present tumor antigens in the cell surface MHC molecules to T cells [17]. The T cells initiate an adaptive immune response resulting in antibody production and the expansion of cytotoxic T cells. These are delivered to both the primary and metastatic tumor sites. Increased trafficking of CD8+ T cells to both irradiated tumor and their draining lymph node has been demonstrated [17, 18]. Furthermore, SABR causes a dose-dependent increase in MHC I tumor neo-antigen presentation by the tumor cells [19]. This, in conjunction with a demonstrated increase in FAS death receptors on the tumor cell surface in response to radiation, renders tumor cells particularly susceptible to CD8+ T cell-mediated cytotoxic attack [20, 21].

There is also evidence from both pre-clinical and clinical studies that radiation, specifically at ablative doses typical of SABR, initiates and augments an immune response and can synergize with immunotherapy [18, 22-25]. In the clinic, this effect of SABR has been documented by multiple case reports of the abscopal effect, where SABR to one site results in a systemic response with tumor regression at untreated metastatic sites [26-28] including that in

mRCC [29]. *In vivo* animal studies have demonstrated that this abscopal effect of SABR is immune-mediated [30]. The abscopal effect of SABR was shown most recently by Postow et. al. in their NEJM report demonstrating that the abscopal effect was due to an increase in tumor-specific T-lymphocytes and a decrease in MDSC following the combination treatment of SABR and CTLA-4 immunotherapy (Ipilimumab) in metastatic melanoma patients [28]. The team noted a temporal association of events with tumor shrinkage associated with antibody responses followed by changes in peripheral-blood immune cells, and a corresponding increase in antibody response to other antigens after radiation therapy.

1.3 PD-1 inhibitor (Nivolumab)

Although HD IL-2 remains a first-line therapy for clear cell mRCC patients, only a small minority of patients exhibits complete response (CR). Educating the immune system by the means of immune-stimulatory treatment to eradicate the primary as well as metastatic tumors may be a promising strategy for this patient population. Immunotherapy such as Nivolumab, which provide a non-specific immune stimulation by blocking immune checkpoints, have shown promise in early phase trials in inducing a cancer-specific immune response in certain metastatic cancer sites [31] and has recently been shown to improve overall survival in mRCC patients who have failed at least one prior anti-angiogenic therapy compared to Everolimus [5].

Nivolumab (BMS-936558; MDX-1106; commercial name Opdivo) is a fully human IgG4 programmed death receptor 1 (PD-1) immune checkpoint inhibitor antibody. It selectively blocks the interaction between PD-1, expressed on immune cells, and PD ligand 1 (PD-L1) and 2 (PD-L2), expressed on tumor cells and immune cells. Normally, this interaction leads to an inhibition in the activation of immune cells and thus would suppress the immune system. By blocking this interaction, Nivolumab activates the immune system. Multiple clinical trials have established the safety and efficacy of Nivolumab for the treatment of advanced or metastatic melanoma and/or renal cell carcinoma [5, 31]. Moreover, it has been recently FDA approved for patients with mRCC who have failed a prior anti-angiogenic therapy.

1.4 Rationale

The combination of Nivolumab immunotherapy and SABR for the treatment of mRCC can be explained by both immunological and clinical rationales.

1.4.1 Immunologic Rationale

Programmed death receptor 1 (PD-1) is a transmembrane protein of the immunoglobulin CD-28 family and is expressed on activated immune cells including macrophages, dendritic cells, activated B and T cells [32]. Two ligands specific for PD-1 have been identified: PD-L1 and PD-L2. PD-L1 is a member of the B7 family costimulatory molecules. Except for some immune cell lineages, human cells do not normally express PD-L1. In addition, while not commonly expressed in tumor cell lines *in vitro*, PD-L1 is widely expressed in various *in vivo* tumor tissues. Multiple studies have shown that interferon-gamma (IFN- γ) produced by activated T-cells induce the over expression of PD-L1 on tumor cells [33]. Tumor cells, induced by IFN- γ , can express high levels of PD-L1, which interacts with PD-1 on immune cells, and through PI3K/Akt inhibition, suppresses their immune response by inducing T cell apoptosis, anergy, exhaustion, dendritic cell suppression, IL-10 production and Treg induction. PD-L1 and PD-1 interaction also protect tumor cells from lysis by cytotoxic T lymphocytes [34]. Given the expression of PD-L1 on host immune cells, anti-body mediated PD-1 inhibition should work in both PD-L1 positive and PD-L1 negative tumors.

As discussed above, Nivolumab blocks the interaction between PD-1 and PD-L1, and thus activates the immune system in a non-specific manner. SABR should be able to provide a specific direction to the immune response by promoting antigen presentation. Recruited and activated by the DAMPs and other changes brought onto the tumor microenvironment by radiation therapy, the APCs migrate to the lymph node for antigen presentation and T-cell activation. RT also increases tumor infiltrating lymphocyte (TIL) trafficking within irradiated tumors [17, 25]. Typically, TILs produce IFN- γ which promotes antigen presentation but at the same time induces PD-L1 expression which is meant to prevent the propagation of the inflammatory

response and limit tissue damage. In the presence of PD-1 inhibitors, INF- γ will enhance antigen presentation and stimulate the immune response without the down-stream effects of PD-1/PD-L1 interaction [35]. Nonetheless, not all PD-L1 expression on tumor cells is IFN- γ -dependent. Certain tumors intrinsically express PD-L1 and certain cancer mutations can also upregulate PD-L1 expression [36, 37].

NK cells are part of the immune system's innate defense against cancer and were first discovered because of their anti-tumor activity [38]. In fact, *ex vivo* expansion and re-infusion of autologous NK cells has shown to induce long-term remission in cancer patients [39]. Specific destruction of cancer stem cells has been demonstrated by NK cells [40]. Radiation therapy increases expression of retinoic acid early inducible-1 (RAE-1) in carcinoma cells, which binds to the NKG2D receptor present in NK cells and CTLs and leads to their activation [25, 41]. Interestingly, NK cells also express PD-1 and it has been shown that PD-1 inhibition enhances NK cell response against multiple myeloma [42]. This suggests another possible synergistic interaction of Nivolumab and SABR in producing an anti-tumor effect mediated by NK cell activation.

Cytoreductive nephrectomy in mRCC has shown to occasionally induce regression of the metastatic foci [43]. It is hypothesized that this is secondary to an immune-mediated response. Two large randomized trials have demonstrated a survival benefit of nephrectomy followed by IFN- α in mRCC patients [44, 45]. In multiple settings, it has been demonstrated that a bulky tumor is able to produce immunosuppressants and induce proliferation of myeloid-derived suppressor cells (MDSCs) leading to immune tolerance of the tumor [46, 47]. The cancer immune surveillance hypothesis states that a tumor is only able to survive and grow large when it has successfully evaded the immune system [48]. Therefore, surgical excision, or in this case ablative radiation of the bulky primary sites of disease can lead to decreased levels of MDSCs, immunostimulation and regression of metastatic foci. In the absence of PD-1/PD-L1 immune check point, a directed immune response against the cancer can flourish.

1.4.2 Clinical Rationale

As applied in concert with Nivolumab in the present study, SABR is intended not only as a systemic cytoreductive agent but also an immunostimulant by antigen presentation. By aggressively cytoreducing the tumor burden, the growth dynamics may be altered to render the remaining cells more susceptible to the immunotherapy, thereby converting more PR patients into CR. Therefore, the purpose of SABR would be three-fold: (1) It would irradiate sites of disease that are bulky and therefore resistant to immunotherapy and potentially serving as origins of further tumor spread and metastasis. (2) By decreasing the burden of disease below a threshold, SABR would reduce or eliminate immunosuppressive effects of tumor. (3) Simultaneously, SABR would act as an *in-situ* tumor vaccination by initiating antigen presentation and immunocyte infiltration, thereby acting synergistically with PD-1 inhibition in facilitating an effective immune response and eventually affecting PR, CR, disease progression and overall survival.

Metastatic RCC can be seen as composed of bulky sites of disease and innumerable micrometastatic foci that are below the resolution limit of radiographic imaging. Systemic therapies like cytokine therapy or newly emerging targeted therapies including PD-1 inhibitors are often effective towards micrometastatic disease but less so to the bulky sites of metastasis which requires multimodality treatment. In a recently published phase 3 RCT comparing Nivolumab to Everolimus in advanced and metastatic RCC patients who have failed at least one anti-angiogenic therapy, the rate of pCR was 1% in the Nivolumab arm and <1% in the Everolimus arm. Therefore, systemic therapies can result in a response, rarely complete, and ultimately the tumors progress, resulting in declining quality of life and death from cancer. Historically, the use of local therapies such as surgical metastasectomy or conventional radiation for a purpose other than palliation was ineffective since the tumor distribution was systemic. RCC is one of the few cancer sites where NCCN guidelines recommend cytoreductive nephrectomy and metastasectomy in selected stage IV patients, not only for palliative purposes but also for potential survival benefit as well. Similarly, RCC is one of the few cancer sites that has demonstrated a survival benefit for metastasectomies. Multiple retrospective studies, and one recently published randomized trial, have demonstrated an overall survival benefit (five years at 32.5% versus 12.4%, $p < 0.001$) of metastasectomy in RCC patients [49-51]. There is growing

evidence that this new, potent, highly focused, and convenient form of radiation called SABR can dramatically debulk and even eradicate bulky tumor deposits as effectively as surgical metastasectomy while being non-invasive [7, 52-54].

Since SABR is shown to be immunostimulatory, and tumor debulking in mRCC has shown to impart survival benefit, the combination of SABR and immunotherapy is expected to be synergistic for mRCC. A combination treatment that offers local control through eradication of bulky progressive sites and simultaneously synergizes with concurrent systemic immunotherapy to eliminate micrometastatic disease is expected to improve outcome dramatically by converting partial responders to complete responders and non-responders into partial responders.

The toxicities of Nivolumab are tolerable and well described. Given the multiple studies demonstrating excellent safety profile of SABR, including our own departmental experience, there are limited concerns for additional toxicity when they are administered sequentially [7-9]. No clinical trials combining SABR with PD-1 inhibitors are published and there is paucity of data regarding the side effect profile of the combination. However, preliminary data from our phase II trial of HD IL-2 (a form of immunotherapy with a serious toxicity profile) and SABR showed that the addition of SABR to immunotherapy did not increase toxicity (data unpublished). A phase I trial of HD IL-2 and SABR in melanoma and RCC patients has proven the safety and feasibility of this regimen [55]. In addition, we have already used SABR in five patients who are receiving Nivolumab for metastatic disease (4 with mRCC and 1 with metastatic melanoma – See table 7.3.1). Our preliminary acute toxicity data (See table 7.3.2), with a follow up ranging between 1 and 3 months, shows that the combination treatment is well tolerated with a favorable toxicity profile comparable to the published side effects of Nivolumab alone (Please see 7.2.2). Please note that the grade 4 toxicity in patient #1 was considered to be due to disease progression in the lung rather than due to the therapy itself.

Therefore, we propose a single institution, safety lead-in phase II trial with SABR to multiple metastatic sites concurrently administered with Nivolumab for patients with metastatic clear cell renal cell cancer who have failed at least one anti-angiogenic therapy. This phase two trial tests the hypothesis that addition of SABR to Nivolumab is a durably effective means of potentiating the effects of PD-1 blockade in inducing higher objective response rate (RR) eventually leading to improvements in progression-free survival, complete response rate, overall survival without degrading quality of life in the mRCC patient population. As reported in prior trials, the RR for Nivolumab (dosing as per the institution guidelines, q 3 weeks until progression) in mRCC is 22%-25% [5, 56]. In the same trials, median OS was 25 months, and PFS was 4-4.6 months. The primary endpoint of this study is to measure improvement in response rate (RR) when SABR is added to Nivolumab compared to the RR in the reported historical control arm with Nivolumab alone. We will propose that the addition of SABR to Nivolumab will increase the RR to 43.8% i.e. 75% increase compared to the historical RR with Nivolumab alone. In our current ongoing phase II clinical trial (STU 012013-041) with similar patient population and treatment strategy of SABR + immunotherapy using IL-2, we are noticing a 53% RR with the combination whereas the historically reported response rate of IL-2 alone treatment is 20% (1). Therefore, we have increased the RR by >150%. Therefore, in oncology clinical trials, it is not uncommon to see such increases since the baseline RR is often low. The secondary objectives of this trial will measure progression-free survival (PFS), overall survival (OS), time to progression (TTP), complete response rate (CRR), duration of treatment response, and health related quality of life outcomes (HR-QoL). In addition, the exploratory objectives will include correlation of the immune response to clinical outcome, evaluation of immunologic biomarkers to predict response and explore possible mechanism of immune resistance. This will help us identify patients who may be more responsive to this regimen. Given the high cost of Nivolumab, it would be also interesting to evaluate the cost-effectiveness of adding SABR upfront with the hope that it would have cost saving effects and improve the quality-adjusted life-years for patients.

1.5 Correlative Studies

The correlative studies will explore the mechanisms of possible immune enhancement by SABR. Activation of the immune response will be evaluated separately utilizing different assays. The humoral response will be evaluated using ELISA to measure the titer of tumor-specific

antibodies generated by SABR and Nivolumab against tumor tissue collected from the respective patients and established human renal cancer cell lines Caki-2 (clear cell) and ACHIN (adenocarcinoma). An overall increase in tumor antigen-specific antibody will be measured using immunoblotting with patient sera as a source of primary antibody.

Enhancements of increased cytotoxicity to renal cancer cells can be measured by cytotoxicity assays. Antibody-dependent cell-mediated cytotoxicity (ADCC) measures the cell-killing ability of certain lymphocytes that require the target cell to be marked by an antibody and thus measures the humeral response [57]. On the other hand, lymphocyte-mediated cytotoxicity assay will measure the formation of tumor-specific CTLs among the lymphocytes collected from patients before and after SABR and Nivolumab. Since it is not practical or feasible to obtain sufficient quantities of tumor cells from each patient to quantitatively assess cytotoxicity by these assays, established allogenic human renal cancer cell line Caki-2 and ACHIN will be used for this purpose. It is a generally accepted principle of tumor immunology that there will be many common tumor antigens between different patient tumors of same site origin, and therefore tumor cell lines as well [57]. In fact, the tumor antigens (PSA, CEA, CA 19-9 etc.) that are in clinical practice are reported to be present in a significant portions of patients of the respective tumor site. This concept of commonality of tumor antigens between allogenic tumor cell lines and patients is put into clinical practice by the GVAX anti-tumor vaccine which is currently in early phase clinical trials for pancreatic, melanoma and renal cancer [58, 59]. GVAX consists of multiple human tumor cell lines of the respective site that is modified to express GM-CSF, and killed with radiation prior to injection in patients. The presence of common tumor antigens in the cell lines and patient's tumors, leads to induction of an immune response. The LNCaP and PC-3 cell lines has been shown to express many of the common renal cancer antigens, and therefore, is an appropriate surrogate to be used instead of patient's own cells and has been used in similar *in vitro* cytotoxicity assays [60-64].

Cytokines are hormonal messengers responsible for most of the effects in the immune system such as activation of innate versus adaptive immune response, cellular versus humoral immune response [65, 66]. For example, an increased level of IL-2 and IFN- γ suggests activation of Th1 cells leading to activation of macrophages and suggests a cell-mediated adaptive immune response whereas IL-4 and IL-5 may indicate Th2 activation and induction of humoral immunity [57, 66]. An increase in IL-17 may suggest activation of autoimmune responses [67]. Therefore, measurements of serum cytokine levels have generally been used previously in clinical trials as surrogates to assess specific activation of immune pathways [68, 69]. Serum cytokines from this clinical trial before and after SABR and at different time-points of Nivolumab administration will be measured using an extensive array of cytokines to explore the specific immune pathways that are initiated/inhibited by our treatments. The planned array of cytokines will measure levels of the following cytokines at different time points for each patients: Th1/Th2/Th17 cytokines: IFN- γ , IL-1 β , IL-2, IL-4, IL-5, IL-8, IL-10, IL-12p70, IL-13, IL-17 TNF- α ; pro-inflammatory cytokines: GM-CSF, IFN- γ , IL-1 β , IL-2, IL-6, IL-8, IL-10, IL-12p70, TNF- α ; Chemokines: Eotaxin, MIP-1 β , TARC, IP-10, IL-8, MCP-1, MCP-4, KC, and others including IL-6, IL-12, TGF- β and HMGB1.

Many surrogate markers for activated and proliferating lymphocytes have been described. Some of these markers include CD25, CD71, CD45RO, CD107a, CD54, CD69, Ki67 and ICOS/CD278 [70-73]. These markers are easily measured with specific antibodies tagged with a fluorophore utilizing FACS analysis. Also using FACS, activation markers such as CD80 and CD 86 on DCs, and inhibitory markers such as PD-1, can be measured as surrogates of immune activation or inhibition. These measurements from PBMCs collected from patients will give us further information regarding the intensity of the immune response.

The relative levels of different monocyte subpopulations in the tumor biopsy sample after treatment as well as in the peripheral circulation often dictate the overall outcome of an immune response, and has been reported in previous immunotherapy trials [55]. Exploration of possible mechanisms of treatment failure can be explored from this analysis as well. Therefore the following subpopulation of cells will be quantified in patient PBMCs (and in tumor biopsy samples where applicable) collected before and after treatment utilizing some of the listed markers specific for those cells:

Immune Cells	Markers
--------------	---------

Lymphocytes	
Cytotoxic T Lymphocyte (CTL)	CD3, CD8
NK	CD3-, CD8, CD16, CD56, CD11b
NKT	CD3, CD16, CD1d
Helper T Cells	CD3, CD4
Th1	IL-18 receptor α , CXCR3, T cell Ig domain, TIM-3, T-bet
Th2	T1/ST2, TIM-1, TIM-2, GATA-3
Th17	Unknown, differentiated by IL-17 production, ROR- γ T
Treg	CD4+CD25+FoxP3+
Memory T Cells	CD45RO
TCM	CD4/CD8, CD62L, CCR7
TEM	CD4/CD8, CCR7-, CD45RA-, CD27
B Cells	CD19, mIg, FcR, CR, CD3-, HLA-DR
MDSC	CD14+, CD11b, CD33, CD 15, CD4, CD8-, HLA-DR-/low
Neutrophils	FcR, CR-, CD3-, HLA-DR-, GR-1 ^{high} , CD11b, Ly6G
Macrophages	FcR, CR, HLA-DR, GR-1 ^{mid}
DC	
Myeloid DC-1	CD11c, TLR2, TLR4
Myeloid DC-2	CD 141, TLR2, TLR4
Plasacytoid DC	CD303, TLR7, TLR9

Table 1: PBMC subpopulations and their markers.

Additionally, we plan to specifically quantify the expression of PD-L1 in all tumor samples from patients' pre-treatment tumor biopsies. Tumor PD-L1 membrane expression ($\geq 1\%$ vs. $< 1\%$ and $\geq 5\%$ vs. $< 5\%$) will be quantified in sections which have at least 100 tumor cells as assessed with immunohistochemical staining. It has been shown previously that tumors with higher PD-L1 expression have worse outcomes but it remains to be shown whether these tumors respond better to anti-PD-1 therapy. It would be very interesting to examine the correlation between PD-L1 expression and tumor response to the combination therapy.

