- 9.2.4 Chromium Release Cytotoxicity Assays:** For cell-mediated cytotoxicity analysis, A 50 µl sample of ⁵¹Cr-labeled target cells (Caki-2 and ACHIN human renal cancer cells) is mixed with 100µl of effector cells (patient PBMC) at various target to effector ratio (E:T ratios). After centrifugation at 100 X G, the cells are incubated for 2 hr at 37°C. The radioactivity of culture supernatant is measured using a gamma counter and percentage of cytotoxicity is calculated. For antibody-dependent cytotoxicity analysis this procedure will be performed with patient's plasma instead of PBMC and the percentage of cytotoxicity is calculated in similar manner. An alternate and non-radioactive labeling method utilizes GAPDH enzyme release from lysed cells called Bioluminescence Non-Radioactive Cytotoxicity Assay (aCella-TOX, T Cell Technology, INC) [108, 109].
- 9.2.5 Flow cytometric analysis (FACS):** For FACS analysis of cell-surface molecules, the cell samples are stained with fluorescent dye – conjugated monoclonal antibodies against the selected markers on ice followed by fixation with 4% paraformaldehyde. Data are acquired on a LSRII (BD Biosciences) and analyzed using FACSDiva software (BD Biosciences). The PBMC of each patient before and after treatment will be analyzed to identify the relative sub-population of CTLs, regulatory T-Cells, effector memory T cells, MDSCs, neutrophils and NK cells utilizing appropriate cell surface markers.

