- 9.2.6 Immunohistochemical staining (IHC):** Standard immunohistochemistry staining procedure for will be performed using the Benchmark XT automated stainer (Ventana) for both antibodies. Briefly, formalin-fixed, paraffin-embedded tissue sections will be cut at 3-4 micron and air-dried overnight. The sections will be deparaffinized, rehydrated, and subjected to heat-induced epitope retrieval. Sections will then be incubated with appropriate primary antibody. For signal detection, ultraView universal detection system (Ventana) will be used. The slides will be developed using 3-3'-diaminobenzidine chromogen and counterstained with hematoxylin. Appropriate positive and negative controls will be utilized for each run of immunostains. The evaluation of the immunostaining will be carried out by a genitourinary pathologist without knowledge of any clinicopathologic data. Only nuclear reactivity will be considered positive. An H score will be assigned as the product of average intensity of staining (0 for negative, 1 for weakly positive, 2 for moderately positive, and 3 for strongly positive) and extent of immunoexpression (0-100% percentage of cells staining). In addition, Dual-antibody ISH will be performed to identify and analyze TILs, CTL (CD3+,CD8+), Tregs (CD4+FoxP3), DC (CD11c) , NK/T (CD3+, CD1d), neutrophils (CD11b, Ly6G} and MDSC (CD14+,CD11b) in the tumor tissue before and after treatment, when available. PD-L1 expression will be quantified from biopsies of tumors prior to treatment.

9.2.7 Serum Cytokine Analysis: Multiplex cytokine analysis in patient's plasma will be performed in precoated 96 well plates (Human TH1/TH2 10 plex ultrasensitive assay, Meso Scale Discovery – MSD, Maryland, USA) according to manufacturer's instructions. 25 µL of diluent 2 is dispersed into each well. The plate is sealed and incubated by vigorous horizontal shaking for 30 minutes at RT.

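### The tumor stain in 9.2.6 labels cells as MDSC on CD14 and CD11b alone, so it cannot apply the HLA-DR criterion that Table 1 lists for MDSC

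*Combined protocol and SAP*

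**What the plan says.** Table 1 in section 1.5 gives the MDSC markers as "CD14+, CD11b, CD33, CD 15, CD4, CD8-, HLA-DR-/low". Its macrophage row begins "FcR, CR, HLA-DR, GR-1". The text above the table applies it to blood mononuclear cells (PBMC) and, where applicable, to tumor biopsies, with samples "collected before and after treatment utilizing some of the listed markers specific for those cells".

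Section 9.2.6 describes the tissue method: "Dual-antibody ISH will be performed to identify and analyze TILs" and several named cell types. The list ends "and MDSC (CD14+,CD11b) in the tumor tissue before and after treatment, when available". It has no macrophage or monocyte entry.

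Section 9.2.5 covers flow cytometry of PBMC before and after treatment. It names the populations but not the gates: "MDSCs, neutrophils and NK cells utilizing appropriate cell surface markers".

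The immunologic rationale in 1.4.1 says that ablating bulky disease "can lead to decreased levels of MDSCs, immunostimulation and regression of metastatic foci".

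**The concern.** HLA-DR is the one marker that Table 1 gives for both MDSC and macrophages, and it gives it opposite status. The tumor stain leaves it out. A cell positive for CD14 and CD11b is called an MDSC in tissue whatever its HLA-DR status, and no other category in 9.2.6 would take up the HLA-DR-positive myeloid cells.

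What is at stake is a mechanistic reading. A fall in MDSC is one strand of the rationale in 1.4.1, and section 1.5 intends the cell subpopulations to help explain treatment failure. If the tissue count moves, or fails to move, the plan as written would report that as a change in MDSC, although the stain cannot show which cells changed.

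**Working it through.** The plan gives no figure to reproduce here. The check compares the marker lists and then asks whether another assay covers the gap.

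**1. Marker lists side by side**

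| Source | Cell type | Markers |
|---|---|---|
| Table 1 | MDSC | CD14+, CD11b, CD33, CD15, CD4, CD8-, HLA-DR negative/low |
| Table 1 | Macrophages | FcR, CR, HLA-DR, GR-1 mid |
| 9.2.6, tumor | MDSC | CD14+, CD11b |
| 9.2.6, tumor | Macrophages, monocytes | no entry |
| 9.2.5, PBMC flow | MDSC | not specified |

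Of the seven MDSC markers in Table 1, the tumor stain keeps two and drops five (7 - 2 = 5). The five include HLA-DR, the only marker common to the MDSC and macrophage rows.

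**2. Is the retained pair specific within Table 1?** CD11b is not: the table also lists it for NK cells and neutrophils. CD14 appears only in the MDSC row, but the table has no monocyte row. On the table alone, then, the pair is not shown to overlap with macrophages. That ordinary monocytes and macrophages can carry CD14 and CD11b is general laboratory knowledge, not something the protocol states. What the protocol does show is that its MDSC row adds an HLA-DR condition to those two markers, and that the stain cannot test it.

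**3. Does another assay supply the missing criterion in tumor?** Section 9.1.2.1 sends the pre-treatment cores to pathology and to tumor lysate; none goes to flow. Section 9.1.2.2 freezes cells for flow from the elective 8-week biopsy only. Flow on tumor cells would therefore have a post-treatment value and no baseline. The 9.2.6 stain is the only described measure of tumor MDSC both before and after treatment.

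**4. Which analyses use the result?** In the objectives, MDSC is named only in exploratory objective 2.3.2, as DC-HIL expression. Section 11.3 names no test of a tissue MDSC count. The post-treatment biopsy is elective (5.1.14.2), and a new baseline biopsy is not required when an earlier metastatic biopsy exists (5.1.14.1).

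**The case against.** The strongest reply is that section 1.5 expressly lets the laboratory use some of the listed markers, that Table 1 is captioned for PBMC, and that CD14 and CD11b both come from its MDSC row. On that reading the tissue pair is a permitted choice. This stands as far as it goes, and it is why the two sections do not flatly contradict each other. It does not make the pair specific: a subset without HLA-DR cannot apply the criterion on which the table's MDSC and macrophage rows differ.

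A second reply is that blood MDSC are measured before and after treatment by flow, and that 1.4.1 speaks of MDSC levels without saying they must be intratumoral. This also stands. It is the reason the remedy can rely on flow, provided the gate is written down.

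A reader might infer more: that ordinary macrophages are in fact being counted as suppressor cells, that the tissue count mostly tracks them, or that a true fall would appear as a rise. The documents do not support this. They give neither the share of CD14+CD11b+ cells that are HLA-DR-positive nor any expected change in either population. Purely as an illustration, let *s* be that share, *m* the change in those cells and *d* the change in MDSC:

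apparent change = *s* x *m* + (1 - *s*) x *d*

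Assume *d* = -50%, and *s* = 90% with a range of 70% to 95%.

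- With *m* = 0, the count changes by 0.10 x (-50%) = -5% (range -15% to -2.5%). The signal is diluted but the sign is right.
- With *m* = +20%, it changes by 0.90 x 20% - 0.10 x 50% = +13%. At *s* = 70% the result is 14% - 15% = -1%, and at *s* = 95% it is 19% - 2.5% = +16.5%.
- With these values of *d* and *m*, the sign reverses only when *s* exceeds 0.50/(0.20 + 0.50), about 71%.

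Every input is assumed, so these figures show how ambiguity could arise, not how large it is.

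**Conclusion.** The point holds in a limited form. The tumor stain cannot apply the HLA-DR condition that Table 1 lists for MDSC, so a tissue count based on it should not be read as an MDSC count. This follows from the marker lists alone. That the pair also captures HLA-DR-positive myeloid cells in practice rests on general laboratory knowledge, and the extent is unknown.

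Severity is low. The consequence is confined to exploratory correlative work with optional post-treatment tissue. The response-rate endpoint, the sample size and the safety rules do not depend on it. It is still worth correcting, because a small wording change prevents a mechanistic conclusion that the assay could not support.

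**What to change.** - **9.2.6:** report the result of this stain as CD14+CD11b+ myeloid cells, and state that no conclusion about tissue MDSC will be drawn from it.
- **9.2.5:** state that MDSC are gated HLA-DR negative or low, as in Table 1, and that MDSC conclusions rest on this flow analysis.
- **Optional:** add HLA-DR to the tissue stain if the laboratory can score it reliably. In a two-antibody stain it would have to take the place of CD14 or CD11b, and a cut-off for low expression would have to be fixed in advance, since the documents give none. Counts would also be less comparable with work based on CD14 and CD11b.

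The first two changes cost a label and a sentence, with no extra tissue or reagents. The loss is that the trial could make no before/after claim about MDSC inside the tumor from the present stain; flow would support such a claim for blood only.
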